- i. **Aim 1:** Feasibility and Acceptance of NEW Tx in the Nonrandomized Trial (N=6). *Hypothesis 1a:* A preliminary study of whether NEW Tx will be feasible with regards to recruitment, retention, blinded assessments, and therapist adherence to NEW Tx⁴³. *Hypothesis 1b:* Participants will report high satisfaction with the treatment (CSQ-8) and acceptability (NEW Tx Scale) over the study duration (i.e., 20-weeks) in a nonrandomized trial ($n = 6$).
- ii. **Aim 2:** Feasibility and Acceptance of NEW Tx and its Evaluation in the Randomized Pilot Trial ($n = 40$). *Hypothesis 2a:* A pilot study of whether NEW Tx will be feasible with regards to recruitment, randomization, retention, blinded assessments, and therapist adherence to NEW Tx⁴³. *Hypothesis 2b:* Participants will report high expectations for the treatment (CEQ) and high satisfaction and acceptability with the treatment (CSQ-8; Post-Tx Questionnaire; NEW Tx Scale) in a 20-week nonrandomized trial ($n = 6$).

B. Exploratory Aims

- i. **Aim 3a:** Reducing Medical Burden in the Randomized Pilot Trial. Pilot test ($n = 40$) the efficacy of NEW Tx in improving medical burden using the Framingham Risk Score (FRS). *Hypothesis 3a:* Over the course of 20-weeks (18 sessions) the NEW Tx group will have a lower FRS compared to treatment as usual (TAU) in the randomized pilot trial.
- ii. **Aim 3b:** Symptoms and Functioning in the Randomized Pilot Trial. Examine the efficacy of NEW Tx in improving functioning and symptoms of BD. *Hypothesis 3b:* Over the course of 20-weeks (18 sessions) the NEW Tx group will improved functioning (LIFE-RIFT) and symptoms (YMRS, MADRS) compared to TAU in the randomized pilot trial.
- iii. **Aim 3c:** Moderator and Mediator of NEW Tx in the Randomized Pilot Trial. Investigate a potential moderator and mediator of treatment response. *Hypothesis 3c.1:* Individuals with higher baseline BMI (>30) will moderate the between treatment effect size for medical burden (FRS) in the randomized pilot trial, such that of NEW Tx will have lower FRSs. *Hypothesis 3c.2:* Mastery of the diet (food diaries) and exercise (exercise duration from Exercise Questionnaire) modules of NEW Tx will mediate the association of NEW Tx and improvement in medical burden (FRS).

III. INTERVENTION MODULES AND OVERVIEW

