- ii. **Phase II:** In this phase, we will pilot test the NEW Tx methods compared to TAU ($n = 60$) to further examine feasibility, to estimate an effect size, and to explore its efficacy for reducing medical burden. TAU will be the control group in the Phase II pilot study as it is the standard treatment in the Massachusetts General Hospital (MGH) Bipolar Clinic and Research Program. Participants randomized to TAU who complete the first 20 weeks of the study will have the option to receive NEW Tx. TAU participants who chose to receive NEW Tx (the waitlist group) will follow the same procedures as the NEW Tx group over an additional 20 weeks such that they will have assessments at Weeks 30, (mid-treatment), 40 (post-treatment), and 52 (follow-up) (see Table 2). For TAU, medication and dosage changes are allowed as long as the change is recommended based on the guidelines and participants remain on a mood stabilizer. Medication changes will be monitored with the Clinical Monitoring Form Medication Module. All participants will have a three-month follow-up visit during which post-treatment measures and assessments will be repeated. Participants will be recruited with the same criteria as the nonrandomized trial, but will be randomized using a 1:1 allocation ratio with a blocking strategy. The assessments will be similar to those used in Phase I. In addition to the study staff utilized in Phase I, clinicians with training in CBT and mood disorders will be added as NEW Tx therapists.

B. Participant Selection and Recruitment

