The independent evaluators will receive instructions and observe the other trained independent evaluators in the BCRP, who have extensive experience in administering the study assessments.

E. Clinician Training

New therapists utilized in Phase II of the study will be trained by the PI. The therapists will be required to demonstrate understanding of the theoretical rationale for each module of NEW Tx, knowledge of BD, and proficiency in the strategies and techniques used to achieve treatment goals. Specific training components will include: (1) reviewing the procedures with PI; (2) role playing NEW Tx techniques; and (3) ongoing weekly supervision with the PI to review their sessions.

Some treatment sessions will be taped to ensure treatment integrity. The PI will review selected audio files and give feedback to the NEW Tx therapists. Audio recording is optional, so participants may opt out and still participate in the study. Audio files will be recorded with a microphone connected to a Partners computer. Files will be uploaded and saved directly to the BCRP secure network, they will not be saved as hard copies. Audio files will be labeled with the subjects' study IDs and not their names. Files will be sent to the PI through Partners Secure File Transfer (<http://rc.partners.org/sFTP>).

F. Targeted Enrollment

We expect to recruit a representative sample of Boston, MA, the location of our research site (see Table 3 and Table 4)⁷⁴. We expect that our sample will resemble the general population given that current studies in the MGH Bipolar Clinic and Research Program are meeting or exceeding this minority representation.

Table 3. Minority Representation in Boston, MA

Racial/Ethnic Category	Boston, MA*
Race	
White	76.1%
Black or African American	14.4%
American Indian and Alaska Native	0.4%
Asian	7.8%
Native Hawaiian and Other Pacific Islander	0.1%
Ethnicity	
Hispanic or Latino	10.5%
White Persons, Not Hispanic/Latino	68.1%
Other	21.4%

*Suffolk & Norfolk Counties

Table 4. Expected Enrollment by Race, Ethnicity and Gender

TARGETED/PLANNED ENROLLMENT for Phase I and II Studies (n = 60)				
Ethnic Category	Sex/Gender			
	Females	Males	Unknown or Not Reported	Total
Hispanic or Latino	6	6		12
Not Hispanic or Latino	18	18		36
Unknown (individuals not reporting ethnicity)	6	6		12
Ethnic Category: Total of All Subjects	30	30		60
Racial Categories				
American Indian/Alaska Native	0	0		0

Asian	3	3		6
Native Hawaiian or Other Pacific Islander	0	0		0

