Research staff will enter scale and assessments responses into the REDCap electronic assessment forms. Using 128 bit RSA Secure Socket Layer (SSL) encryption, approved users will be logged-in to machines using secured browsers behind the Partners Healthcare Systems IS corporate firewall or the RIH firewall. Staff will have a unique identifying key that will link them to the electronic study forms. This unique ID will be used in addition to a randomly generated secure password that only the staff person will have. Additional confidentiality procedures are detailed in the Human Subjects section.

B. Statistical Analyses Plan for Research Aims

Each of the statistical tests below will use a two-tailed alpha-level of 0.05.

- i. **Aim 1: Feasibility in Nonrandomized Trial (Phase I).** *Hypothesis 1a:* Descriptive statistics will be used to report the number of intervention sessions attended (we expect > 80%), number of participants recruited per month, and therapist adherence to NEW Tx (average adherence score ≥ 6). *Hypothesis 1b:* Participants will report high satisfaction (total CSQ-8 score, $M > 24^{75}$) with the treatment and acceptability (total NEW Tx Scale score, $M < 25$, or at least an average score of “agree” on half of the items).
- ii. **Aim 2: Feasibility in Randomized Trial (Phase II).** *Hypothesis 2a:* Descriptive statistics will be used to report the number of intervention sessions attended (we expect > 80%), number of participants recruited per month, randomization rate (number randomized/number consented), number of assessment sessions attended (we expect > 80%), and retention (number of study completers/number randomized) (we expect > 80%, which is conservative for diet and exercise interventions for severe mental illness^{25, 76-78}) and therapist adherence to NEW Tx (average adherence score ≥ 6). *Hypothesis 2b:* Participants will report high expectations (CEQ score) for the treatment and high satisfaction and acceptability (CSQ-8, Post-Tx Questionnaire, NEW Tx Scale).

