- iii. **Aim 3: Exploratory Aims (Phase II).** *Hypotheses 3a and 3b:* Between treatment group effects sizes (and 95% CI) will be calculated. To supplement this, Mann-Whitney tests will compare treatment groups on medical burden (as measured by FRS) (*Hypothesis 3a*) and on improvement in symptoms (MADRS, YMRS) and functioning (LIFE-RIFT) (*Hypothesis 3b*) based on change from baseline. *Hypothesis 3c.1:* We will investigate baseline BMI as a potential moderator of treatment response. The focus will be on the magnitude of the effect, not on significance testing. The between treatment group effect sizes (i.e., FRS, MADRS, YMRS, LIFE-RIFT) will be compared with those who have high baseline BMI (> 30) versus low BMI (< 30). *Hypothesis 3c.2:* Mastery of the diet (Nutrition Data System score of food diaries) and exercise (weekly exercise duration from Exercise Questionnaire) modules will mediate the association of NEW Tx and improvement in medical burden (FRS). The

dependent variable will represent change in the FRS score from time of completion of respective module. The mediators will be tested separately. Differential between treatment group effect sizes for those who did and did not master the modules will provide evidence of a mediator of treatment.

C. Rate of Attrition

Some attrition (i.e., 20%) is expected and this can result in bias and reduce power, precision and generalizability⁷⁹. Consistent with the Intent to Treat principle⁸⁰, we will continue with the assessments for the study duration, even among those who fail to comply with the treatment⁸¹. As one aspect of the feasibility study, we will assess the likelihood to attrite using the “Intent to Attend” measure⁷².

D. Power Analysis

The sample sizes for the Phase I and II trials are based primarily on the fundamental aim of this project: feasibility. The N is not based on what is needed for inferential analyses as they are not a fundamental aspect of the design. Power analyses are not indicated for the proposed exploratory analyses. We acknowledge that we will not have sufficient power to detect large effects (e.g., $d = .80$).

IX. REFERENCES

1. Hennekens C. Increasing global burden of cardiovascular disease in general populations and patients with schizophrenia. *Journal of Clinical Psychiatry*. 2007;68(suppl 4):4-7.

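### The planned 95% CIs for the between-arm effect sizes will be too narrow if NEW Tx therapists differ in outcome, because the plan makes no allowance for therapist in the only arm that has them

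*Combined protocol and SAP*

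**What the plan says.** **Analysis.** Section VIII.B, item iii (Hypotheses 3a and 3b) states: "Between treatment group effects sizes (and 95% CI) will be calculated". It then adds a test on change from baseline: "To supplement this, Mann-Whitney tests will compare treatment groups on medical burden (as measured by FRS"), with the symptom and functioning scales handled in the same way. It gives no formula for the effect size or its interval, no therapist term, no ICC, and no rule for assigning patients to therapists.

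**Delivery.** Section IV.A describes NEW Tx as one-to-one sessions. In Phase I the PI treats every patient. In Phase II, on top of the Phase I staff, "clinicians with training in CBT and mood disorders will be added as NEW Tx therapists". Section IV.E adds: "New therapists utilized in Phase II of the study will be trained by the PI", with weekly supervision. Neither the number of therapists nor their caseloads are stated.

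**Control.** TAU is the clinic's standard treatment. TAU patients may take up NEW Tx only after completing the first 20 weeks (section IV.A, Phase II). Patients are "randomized using a 1:1 allocation ratio with a blocking strategy".

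**Purpose.** Section IV.A lists estimation of an effect size among the aims of Phase II. The opening of section III says the modular format is meant to make NEW Tx more generalizable across patients, settings and providers.

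**The concern.** Patients who share a therapist may have more similar outcomes than patients who do not. Here that can happen through NEW Tx therapists in one arm only. An ordinary two-group interval takes every patient as an independent unit, and so does the standard Mann-Whitney variance. If therapists differ, both understate the uncertainty of the NEW Tx arm.

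Some room for therapist differences is visible in the plan. Modules are chosen for each patient (section III), the added therapists are newly trained in NEW Tx (section IV.E), and therapist adherence is itself measured as a feasibility outcome (section VIII.B). None of that variation reaches the interval.

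What is at stake is the stated precision of the effect size, most of all if a later trial is planned from it.

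**Working it through.** The plan states no interval width, ICC, design effect or number of therapists, so there is no figure of its own to reproduce.

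**Inputs from the documents**
- Phase II size: 60 in sections IV.A and IV.B, but 40 in section II (Aims 2 and 3a). With 1:1 allocation this is 30 or 20 per arm.
- Attrition: 20% (section VIII.C), leaving 24 per arm from 60, or 16 per arm from 40.
- Two-sided level: 0.05 (section VIII.B).

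**Assumptions (not in the documents)**
- Number of NEW Tx therapists k: 2 to 5, with equal caseloads m = n/k.
- Therapist ICC: 0 to 0.10, the same for every outcome.
- Equal total variance in the two arms.

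**Formulas**
1. Design effect in the NEW Tx arm: DE = 1 + (m − 1) × ICC. In the TAU arm it is 1.
2. Factor by which the standard error (SE) of the difference must grow: R = √((DE + 1)/2).
3. True coverage of the ordinary 95% CI: 2Φ(1.96/R) − 1.

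**Central case: 30 per arm, k = 3, ICC 0.05**
- m = 30/3 = 10; DE = 1 + 9 × 0.05 = 1.45.
- R = √(2.45/2) = 1.107. The SE must grow by 11%; put the other way, the ordinary SE is 1 − 1/1.107 = 9.7% too small.
- Coverage = 2Φ(1.96/1.107) − 1 = 92.3%. Simulating the ordinary pooled-SD t interval (40,000 runs) gave 92.1%.
- In SD units, the half-width goes from 1.96 × √(2/30) = 0.506 to 0.560.

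**SE growth factor R over the assumed range**

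| Per arm | k | ICC 0 | ICC 0.02 | ICC 0.05 | ICC 0.10 |
|---|---|---|---|---|---|
| 30 | 2 | 1.000 | 1.068 | 1.162 | 1.304 |
| 30 | 3 | 1.000 | 1.044 | 1.107 | 1.204 |
| 30 | 5 | 1.000 | 1.025 | 1.061 | 1.118 |
| 24 | 2 | 1.000 | 1.054 | 1.129 | 1.245 |
| 24 | 3 | 1.000 | 1.034 | 1.084 | 1.162 |
| 20 | 2 | 1.000 | 1.044 | 1.107 | 1.204 |
| 20 | 3 | 1.000 | 1.028 | 1.068 | 1.133 |

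At 30 per arm, coverage runs from 95% (ICC 0) to 86.7% (k = 2, ICC 0.10). With k = 3 and ICC 0.05 it is 92.9% at 24 per arm and 93.3% at 20 per arm. At 16 per arm the same case gives R = 1.053 and 93.7%.

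**Uneven caseloads.** Replace m by Σm²/Σm. Caseloads of 15, 5, 5 and 5 give 300/30 = 10, the same as three therapists with 10 patients each.

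**What a fitted therapist random effect would cost.** Let the NEW Tx mean have variance proportional to DE on k − 1 degrees of freedom, and the TAU mean variance proportional to 1 on n − 1. The Satterthwaite degrees of freedom are (DE + 1)² / (DE²/(k − 1) + 1/(n − 1)). For n = 30, k = 3 and ICC 0.05 this is 2.45² / (1.45²/2 + 1/29) = 6.0025/1.0857 = 5.5. Against the ordinary t interval, the CI then widens by about 38%, not 11%. The same calculation gives 11% (k = 5, ICC 0.02), 181% (k = 2, ICC 0.10, about 2 degrees of freedom), and 17% with k = 3 even when the ICC is 0.

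**The case against.** **The premise is conditional.** A reader might infer that the intervals are too narrow as a matter of fact. The documents do not support that: it needs an ICC above 0, for which they give no evidence. Common training by the PI, weekly supervision, review of some taped sessions and an adherence target may keep the ICC low. A reader might also infer that the plan states that patients are independent, or that the therapists are few. Neither is written. The first follows only from plain two-group methods and silence on clustering; the second is an assumption. This objection stands and fixes the wording as conditional.

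**The inference target.** The ordinary CI can be read as describing the effect with these particular therapists, and treating the PI and selected trainees as a sample of therapists is a choice. This stands in part. But section III aims at use across providers, and Phase II is meant to yield an effect size, so a reader will take the interval beyond these therapists.

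**PI against the others.** A reader might infer that the pooled effect hides better results in the PI's own patients. The documents give no evidence of that and no method of assigning patients to therapists. A contrast of the PI with the others would rest on few patients each and could be confounded by case assignment. It is not part of this point.

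**Low stakes.** Aim 3 is exploratory, and section VIII.D says that the sample size rests on feasibility and not on inferential analyses. This stands and limits the severity.

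**Conclusion.** The point holds in conditional form and is of low severity. The randomized comparison is nested by therapist in one arm, and the planned intervals make no allowance for it. If therapists differ, those intervals overstate precision.

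The size depends on two unstated inputs. Over 2 to 5 therapists and ICC 0 to 0.10, the SE must grow by 0% to 30% with 30 per arm, 0% to 25% with 24 per arm after attrition, and 0% to 20% with 20 per arm if the total of 40 applies. The effect exceeds about 10% mainly with 2 or 3 therapists and an ICC of 0.05 or more, or with an ICC near 0.10. It falls to nothing as the ICC approaches 0. No confirmatory or feasibility conclusion is affected.

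**What to change.** 1. Record the treating therapist for every NEW Tx patient. This may be hard to recover later.
2. Report the number of therapists and their caseloads.
3. Beside each ordinary 95% CI, show a sensitivity CI with the NEW Tx arm variance multiplied by 1 + (m − 1) × ICC, at ICC 0.02, 0.05 and 0.10. Here m is the caseload, or Σm²/Σm if caseloads are uneven. The ordinary interval serves as the ICC 0 case.
4. Do not make a fitted therapist random effect the main analysis. With so few therapists its variance cannot be estimated reliably, and the CI could widen far more than 30%.
5. Reconcile the Phase II totals of 40 and 60, since every interval width depends on them.

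The cost is one data field, a few sentences in section VIII.B, a little extra analysis, and a somewhat wider sensitivity interval. The design and sample size need not change on account of this point.

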Despite these multiple factors, very few integrated programs have been developed, and only a few have been developed for severe mental illness. The Lifestyle Challenge Program incorporated nutrition, weight-management and exercise strategies into weekly, group-based psychoeducational sessions²⁵. Only 43% of participants completed the program, but of these participants, they reported improvements in health-related quality of life and depressive symptoms²⁵. The Integrated Intervention Model is an individualized psychoeducational program on sleep/wake rhythms, nutrition, exercise, and time management in BD ($n = 24$) and improved overall functioning and reduced psychiatric hospitalizations, but did not examine risk factors for cardiovascular disease²⁶. The medical care model for BD consists of four psychoeducational group-based, self-management sessions about cardiovascular disease and how to improve diet and increase exercise. The treatment group showed improvements in mental health-quality of life and may have buffered against further decline in their quality of life¹⁸. Other current treatments for co-morbid medical and psychiatric conditions focus on establishing co-located general medical providers or treatment teams within mental health clinics^{27, 28}. Although these approaches are targeting medical burden and enhance communication between providers, they tend to be costly, rely on an abundance of resources, or do not develop an individualized, integrated treatment. Without integrated treatments, one provider is not responsible for monitoring the patient which may limit observations of interactions between treatment and conditions^{15, 29}.

The nutrition, exercise, and wellness treatment program (NEW Tx) is designed to reduce medical burden by targeting three areas: poor nutrition/obesity, sedentary lifestyle, and unhealthy lifestyle choices:

- i. **Nutrition:** Individuals with BD have poor eating and nutritional habits^{30, 31}. Moreover, obesity is more prevalent in BD than the general population, with one study finding 38% of bipolar individuals are overweight and 29% are obese³².

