Participants ($n = 6$ for the open trial phase; $n = 60$ for the randomized phase) will be recruited from within as well as outside the MGH Bipolar Clinic and Research Program, and we plan to recruit 1 participant per month for the Phase I open trial and 2 participants per month for the Phase II randomized trial. Some subjects will be self-referred, whereas others will be referred by MGH or community clinicians. Some subjects may be obtained from media advertisements. Potential participants will not be identified through medical records, and the researchers will not contact potential participants without their permission. If a clinician feels that one of his or her patients would be potentially appropriate for this study, the patient will be encouraged to contact the PI or the research assistant directly. Alternatively, the clinician may ask the patient to give permission to be contacted over the phone by either the PI or the research assistant. Written IRB approved informed consent will be obtained from all patients before protocol-specified procedures are carried out.

Patients may be referred to the study by their treating clinicians in the MGH Bipolar Clinic and Research Program, and will be recruited according to the following criteria:

i. **Inclusion Criteria**

- Diagnosis of Bipolar Disorder (Type I or II), which is the primary focus of treatment
- Ability to give informed consent
- Currently ill (CGI-BP ≥ 3)
- Age > 18 years and < 65 years
- Overweight individuals (BMI > 25); those with BMI of 25-30 must also have high rate of percentage of body fat (greater than or equal to 32% for women and 25% for men)

ii. **Exclusion Criteria**

- Unwilling/unable to comply with study procedures
- Endorsed item, confirmed by patient's physician, on the PAR-Q
- Euthymic (CGI-BP < 3)
- Diagnosis of anorexia nervosa or bulimia nervosa in the past month
- Diagnosis of substance dependence in the past month
- Active suicidality (MADRS item 9 score > 4)
- Pregnant (as analyzed by a urine pregnancy test)
- Exercising regularly (i.e., 5 days per week for 30 min)
- Neurologic disorder or history of head trauma
- Contraindications to exercise or diet interventions (e.g., co-morbid nutritional and metabolic diseases, physical injuries)

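### Hypothesis 3c.1 judges BMI moderation only by a split at 30, with no interval for the difference and no group for a BMI of exactly 30; a continuous-BMI estimate should be added beside it

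*Combined protocol and SAP*

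**What the plan says.** Section II.B (Aim 3c) states the hypothesis by category: "Individuals with higher baseline BMI (>30) will moderate the between treatment effect size for medical burden (FRS"). Section VIII.B carries this out by forming two groups, "high baseline BMI (> 30) versus low BMI (< 30"), and setting their results side by side: "The between treatment group effect sizes (i.e., FRS, MADRS, YMRS, LIFE-RIFT) will be compared". On inference it says: "The focus will be on the magnitude of the effect, not on significance testing".

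The same paragraph attaches a 95% CI to the between-arm effect sizes for Hypotheses 3a and 3b. For 3c.1 it mentions no interval, no method of comparison, no interaction term and no analysis with BMI left continuous.

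The inclusion criteria in section IV.B bear on the split. Entry requires "Overweight individuals (BMI > 25"), and "those with BMI of 25-30 must also have high rate of percentage of body fat", with thresholds of 32% for women and 25% for men. That extra filter does not apply above 30.

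**The concern.** The plan says that the size of the moderation is what matters, so the precision of that size is what the analysis should protect. A two-group split treats a BMI of 31 like one of 45, and 29.9 as different from 30.1. If the effect changes gradually with BMI, this discards usable information from a sample that is already small. Two subgroup effect sizes shown without an interval on their difference can also differ widely by chance and be read as moderation, and this is repeated over four outcomes.

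A smaller matter is that both inequalities are strict. An eligible participant at exactly 30, whom the entry criteria place in the 25-30 band, has no analysis group.

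**Working it through.** The plan gives no precision or information figure for 3c.1, so there is nothing to reproduce.

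**Inputs from the documents.** The cutpoint is 30 and entry is above 25. Phase II N is 60 in section IV.A and 40 in section II. Allocation is 1:1 and expected attrition is 20%, so completers number 60 × 0.8 = 48 or 40 × 0.8 = 32. The only BMI distribution figure is background literature in section I: "38% of bipolar individuals are overweight and 29% are obese". From it, 29/(38 + 29) = 43% of those above 25 are obese, before the body-fat filter.

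**Information lost by the split.** For a linear arm-by-BMI effect, loss = 1 − r², where r is the correlation between BMI and the indicator BMI > 30. For a normal BMI with share p above 30, loss = 1 − φ(z_p)²/[p(1 − p)]. At p = 0.5 this is 1 − 0.3989²/0.25 = 36.3%, the minimum for that shape. It is 37.0% at p = 43% and 51.0% at p = 80%.

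The sample is truncated at 25, so the loss was also simulated. The source population was matched to the 38% and 29% figures, and 100% down to 25% of the overweight stratum was kept to mimic the body-fat filter (an assumed range):

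| Assumed BMI above 25 | Share above 30 | Loss |
|---|---|---|
| Truncated normal, all overweight kept | 43% | 33.5% |
| Truncated normal, a quarter kept | 75% | 47.7% |
| Truncated lognormal, all kept | 43% | 37.3% |
| Truncated lognormal, a quarter kept | 75% | 54.0% |
| Uniform 25-35 | 50% | 25% |
| Shifted exponential, mean 31 to 35 | 43% to 61% | 47% to 62% |
| Shifted gamma, mean 31 to 35 | 50% to 74% | 45% to 65% |

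The first four rows, tied to the documents' only BMI figure, give about a third to a half. At 48 completers the split then carries the information of 48 × (1 − 0.335) = 32 down to 48 × (1 − 0.540) = 22 people analysed with continuous BMI. Relative to the effect, the interval is 1/√0.665 = 1.23 to 1.0/√0.460 = 1.47 times as wide.

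**The reverse case.** The same r² governs a true step at 30. There the continuous term loses 1 − r² and the split loses nothing.

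**Precision of the planned contrast.** With 1:1 allocation and effect sizes near zero, the 95% half-width for the difference between subgroup effect sizes is 1.96 × √(4/n₁ + 4/n₂), where n₁ and n₂ are the BMI group totals.

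- 48 completers, equal groups: 1.96 × √(4/24 + 4/24) = 1.13.
- 48 completers, 80% above 30: 1.96 × √(4/38.4 + 4/9.6) = 1.41.
- 32 completers, equal groups: 1.96 × √(4/16 + 4/16) = 1.39.
- 32 completers, 80% above 30: 1.96 × √(4/25.6 + 4/6.4) = 1.73.

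These widths mainly reflect sample size. They show why an interval must be reported; they do not measure harm done by the split.

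**Participants at exactly 30.** Under the lognormal with no filter, about 0.9% fall at 30.0 if BMI is recorded to one decimal (60 × 0.009 = 0.5 people). About 9% do if BMI is rounded to whole numbers (60 × 0.093 = 5.6 people).

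**Influence on the continuous slope.** In simulated samples of 32 and 48 from the lognormal, gamma and exponential shapes above, the 3 to 5 participants furthest from the mean supplied about 0.4 to 0.6 of the BMI sum of squares.

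**The case against.** The strongest case for the plan is that its hypothesis is itself stated in terms of BMI above 30, and the split answers it directly. If moderation really is a step there, the split is the efficient analysis and a straight line is the wrong model. Nothing in the documents favours a linear effect over a threshold. This stands, and it is why the split should be kept.

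It also stands that the analysis is a sub-hypothesis of an exploratory aim in a feasibility pilot, that significance testing is disclaimed, and that section VIII.D does not claim power. The gap at 30 is close to editorial, since the hypothesis and the entry band both point to 30 belonging with the lower group.

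The continuous model has a cost. A few very heavy participants can drive its slope, and a plot is a weak check of linearity with 16 to 24 completers per arm.

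Some stronger readings are not supported:

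- A reader might take a particular percentage loss as a fact about this trial. The documents give no BMI mean, SD or expected share above 30 for the sample, and the loss holds only for a near-linear effect.
- A reader might infer that the subgroups will be compared by eye. The text says only that they will be compared; what is missing is a stated method and interval.
- A reader might think that continuous BMI cures the body-fat selection. It does not: the kind of participant enrolled changes at 30, and a line fitted across that point carries the same confounding.

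What the objection does not answer is that a plan focused on magnitude gives no interval for the magnitude it will report and makes no use of the BMI values within each group.

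**Conclusion.** The point holds as a minor improvement. The text establishes the split as the sole analysis, the absence of a stated interval for the difference, and the unassigned value at 30. The loss of about a third to a half is conditional on near-linear moderation and on a normal or lognormal BMI truncated at 25 and matched to the background prevalence figures, with 43% to 75% of the sample above 30. Other shapes widen it to about 25% to 65%, and it vanishes for a step at 30. A continuous estimate recovers that loss if moderation is linear but remains imprecise with 32 to 48 completers. The feasibility aims and the main between-arm comparisons are not affected.

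**What to change.** In section VIII.B, under Hypothesis 3c.1:

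1. For each of the four outcomes, fit a model of the Week 20 value on arm, its baseline value, baseline BMI and arm by BMI. Report the interaction coefficient with a 95% CI, and the fitted arm effect with its CI at two or three prespecified BMI values.
2. Keep the split at 30 as a companion display, since it matches the stated hypothesis. Define the groups as > 30 and ≤ 30, and give a 95% CI for the difference between the subgroup effect sizes.
3. Show a plot of outcome against BMI by arm, and report how the slope changes when the most influential observations are left out.
4. State that body fat was an entry condition only for BMI 25-30, so neither analysis isolates BMI from that selection.

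The cost is a few lines of SAP wording and modest programming. No new data, visits or participants are needed. The price is a near-linearity assumption and sensitivity to extreme BMI values, which the split display and the influence check put in view but do not remove.
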